The above health states are progressive, but it is not required for all patients to go through all the 5 states. For example, for patients without disease progression on the initial treatment, they will not enter TOX2, TWiST2, and PROG states.

The Q-TWiST score is obtained by summing the weighted clinical health state durations. The Q-TWiST score for each treatment arm will be calculated using the following formula:

$$Q-TWiST = (u_{TOX1} \times TOX1) + (u_{TWiST1} \times TWiST1) + (u_{TOX2} \times TOX2) + (u_{TWiST2} \times TWiST2) + (u_{PROG} \times PROG)$$

where u_{TOX1} , u_{TWiST1} , u_{TOX2} , u_{TWiST2} , u_{PROG} represent the average group utility weight for each health state for that arm; TOX1, TWiST1, TOX2, TWiST2, and PROG represent the mean duration of the health state of that arm.

In the Q-TWiST analysis, each health state is assigned a weight ranging from 0 (representing death) to 1 (indicating perfect health). These weights are called utility scores as well. For each patient, EQ-5D will be administered multiple times (at baseline, at each cycle while during the initial and subsequent treatment period, then every 3 months up to 2 years from study entry if patients are off protocol

treatment and not receiving non-protocol therapy, at end of treatment in each step (before and after crossover), and at dose modification) and its score will be used to derive the utility score. In this study, the utility score is conditional on the patient-reported health state on the 5 dimensions (mobility, self-care, usual activities, pain/discomfort, anxiety/depression) captured in EQ-5D. A number ranging from 1 to 5 will be assigned to each level in each of the 5 dimensions. A patient's health state thus can be labeled using a 5-number descriptor ranging from 11111 to 55555. A utility score corresponding to each possible descriptor elicited from general population samples (by country) was provided in the file "EQ-5D-5L_Crosswalk value sets" posted in the website of www.euroqol.org.⁴⁶ We are going to use the value set elicited from US subjects for our patients in this study. For instance, a health state with a descriptor of "11111" is given a utility score of 1.000, "12111" is assigned a utility value of 0.854, and "43333" is with a utility score of 0.573.

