The average EQ-5D utility score for a patient's individual health state will be computed across all utility scores collected during that health state. For instance, EQ-5D scores for all visits during which a grade 3 or 4 adverse event is reported before the patient experiences disease progression on initial treatment will be averaged to form that patient's TOX1 utility score. All EQ-5D scores for visits without either grade 3 or 4 adverse events or disease progression on initial treatment will be averaged to form the patient's TWiST1 utility score. Similar definition and computation apply for TOX2 and TWiST2 with respect to the subsequent treatment. All EQ-5D scores for visits after last disease progression will be averaged to form that patient's PROG utility score. For each health state, the average group utility score is the mean of that health state within each treatment arm.

The restricted mean amount of time for each health state will be estimated using the Kaplan-Meier method, with time limit set at 2 years for computation of all restricted means. The duration of each health state is defined as follows:

- Mean duration of TWiST1 = mean PFS1 – mean TOX1,
- Mean duration of TWiST2 = mean PFS2 – mean TOX2,
- Mean duration of PROG = mean OS – mean PFS2,

where PFS1 is defined as the time from study entry to the first disease progression on the initial treatment. For patients alive without first disease progression, PFS1 will be censored at the date of last disease evaluation in step 1. PFS2 is defined as the time from study entry to the second disease progression on the subsequent treatment (in step 2). For patients enrolled into step 2, if they are alive without disease progression in step 2, PFS2 will be censored at the date of last disease evaluation in step 2. For patients not enrolled into step 2, PFS2 will be censored at the date of last disease evaluation in step 1. OS is defined as the time from study entry to death from any cause, censored at the date of last contact. TOX1 is defined as the days spent with grade 3 or 4 toxicities prior to disease progression on the

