initial treatment (in step 1). For patients with severe toxicities reported in step 1 but no end date reported, TOX1 will be capped at the date of disease progression in step 1 or death without progression. TOX2 is defined as the number of days with grade 3 or 4 toxicities reported after the first disease progression on the initial treatment (in step 1) and prior to the second disease progression on the subsequent treatment (in step 2). For patients with severe toxicities reported during this period but no end date reported, TOX2 will be capped at the date of disease progression on the subsequent treatment or death without progression. For patients not receiving the subsequent treatment, TOX2 is counted as 0.

There are a couple of special notes for this expanded Q-TWiST analysis. If patients die during an early state and EQ-5D is not administered thereafter, the utility score in each of subsequent states will be defined as 0. If patients withdraw or lost to follow-up during an earlier state, the utility score in subsequent states will be assigned 0.. Finally, since Q-TWiST is being computed for 2 years in this study, once the duration of earlier states reach 2 years, the utility score collected in subsequent states will be used for these patients in the 2-year Q-TWiST analysis.

The mean amount of time for each health state and the average group utility scores will be summarized by initial treatment (i.e., arm A: ipilimumab + nivolumab (with subsequent dabrafenib + trametinib) vs. arm B: dabrafenib + trametinib (with subsequent ipilimumab + nivolumab)). The Q-TWiST subscore and the overall Q-TWiST score will then be reported by initial treatment. Differences between treatment groups in the mean Q-TWiST score (including the overall score and the subscore) will be calculated. For each score, a 95% confidence interval (CI) and two-sided P-value for testing the null hypothesis of no difference between treatment groups will be conducted using a Z-test (with normal approximation), with standard errors calculated by the bootstrap method. The bootstrap will be performed by repeated sampling, with replacement, from the sample of patients enrolled in this study, to obtain a new sample. The means for the new sample will be calculated using the same method as described above. This process will be repeated 1000 times. Based on the means obtained by the bootstrap method, the standard errors can be calculated.

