Due to the multiple assessment timepoints for EQ-5D (at baseline, at each cycle while during the initial and subsequent treatment period, then every 3 months up to 2 years from study entry if patients are off protocol treatment and not receiving non-protocol therapy, at end of treatment in each step (before and after crossover), and at dose modification), we do not expect too many patients that reach a state but do not get any EQ-5D evaluation for the utility calculations. If this indeed occurs, it suggests that the reached state is rather short. For the primary Q-TWiST analysis, we assume these data will be missing at random then compute the average group utility weight for each health state based on patients with nonmissing data on the reached

states. If more than 20% of the cases have missing data, with respect to any reached health state, a sensitivity analysis will be performed with missing utility scores on a reached state being replaced by the average EQ-5D utility score from these patients' preceding health state. In case of discrepancies between the primary analysis and the sensitivity analysis, possible explanations will be discussed.

Secondary PRO Analysis. Overall function will be assessed (at baseline, weeks 6 (end of cycle 1), weeks 12 (end of cycle 2), and months 6 (disease stability)) while during the initial and subsequent treatment period (at 6-week, 12-week, months 6, 12, 18, and 24 from study entry (even off study treatment)) using PROMIS PROFILE-29. This instrument, consists of 7 short forms (Depression, Anxiety, Physical Function, Pain Interference, Fatigue, Sleep Disturbance, and Ability to Participate in Social Roles and Activities, with 4 items in each short form) together with one Pain Intensity item. Each item has five response options ranging in value from 1 to 5, except for the Pain Intensity item which has eleven response options ranging in value from 0 to 10. A raw score can be computed for each short form by summing the values of the response to each question within each domain.

The total raw score for each short form can then be converted into a standardized T-score with a mean of 50 and a standard deviation of 10. As to the Pain Intensity item, the raw response (0-10) can be used directly in data analyses.

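### The Q-TWiST zero-utility rule, as written, charges early death and loss a second time through the group weight, and it conflicts with the plan's own averaging rule

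*Combined protocol and SAP*

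**What the plan says.** Section 9.8.2 splits survival into five states (TOX1, TWiST1, TOX2, TWiST2, PROG). Each arm's score is the sum over states of group utility times mean duration.

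- **Durations.** "The restricted mean amount of time for each health state will be estimated using the Kaplan-Meier method", restricted to 2 years. In the OS component death is the event and patients without an event are censored at last contact. TOX2 is set to zero for anyone who never receives the second treatment.
- **Weights.** EQ-5D utilities are averaged within patient and state; then "the average group utility score is the mean of that health state within each treatment arm". On the utility scale, 0 stands for death and 1 for perfect health.
- **Special notes.** For a patient who dies in an early state with no later EQ-5D, "the utility score in each of subsequent states will be defined as 0". Next: "If patients withdraw or lost to follow-up during an earlier state, the utility score in subsequent states will be assigned 0". The last note says that once earlier states have filled 2 years, "the utility score collected in subsequent states will be used for these patients in the 2-year Q-TWiST analysis".
- **Missing data.** For patients who reach a state but have no EQ-5D there, the primary analysis is to "compute the average group utility weight for each health state based on patients with nonmissing data" on the states reached. If more than 20% of cases are missing for any reached state, a sensitivity analysis carries forward the utility from the preceding state.

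Section 9.8.1 makes this the primary PRO comparison. Section 2.4 lists it among the secondary objectives of the trial.

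**The concern.** A patient who dies before reaching a state already adds no time to it, so the penalty for early death sits in the duration. A zero for that patient in the state's mean utility applies the penalty again. The weight then reflects mortality as well as the health of people living in the state.

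For loss to follow-up the two halves of the formula disagree. The durations censor the patient, who may be alive, while the weight would give the value reserved for death.

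The paragraph on missing data points the other way, because it builds the primary weights from patients with data on the states they reached. The text therefore does not settle which calculation is primary. The planned checks do not help: the sensitivity analysis concerns reached states only, and the bootstrap repeats the same calculation in each resample, so it carries any bias along.

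The last note has a separate fault. A state entered after 2 years has no time in the 2-year window, so its utilities have nothing to weight.

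**Working it through.** **The plan's own figures.** The clinically important difference is 10% of a 24-month control median, which is 2.4 months. For 135 per arm and SD 7, the standardised difference is 2.4 / (7 × √(2/135)) = 2.82, and the normal approximation gives power Φ(2.82 − 1.96) = 80.4% (noncentral t: 80.1%). The plan states 80%. All 12 rows of the table in Section 9.8.1 reproduce to within 2 points. The zero rule plays no part in that table.

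**Algebra.** Let u be the mean utility of patients observed in a later state, T the arm's restricted mean time in it, and q the share of averaged values that are assigned zeros.

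- Reached patients only: u × T.
- Zeros averaged in: (1 − q) × u × T.
- Error per state: −q × u × T. The shift in A − B is the sum over later states of q_B u_B T_B − q_A u_A T_A.

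**Worked example (assumed).** Of 100 patients, 20 die in state 1 and 80 spend a mean of 6 months in state 2 at utility 0.75.

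- True contribution per patient: 80 × 6 × 0.75 / 100 = 3.60 months.
- Arm-mean duration: 80 × 6 / 100 = 4.8 months.
- Reached-only weight: 0.75 × 4.8 = 3.60.
- Weight with zeros: (80 × 0.75 / 100) × 4.8 = 0.60 × 4.8 = 2.88, which is 20% too low.

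**Simulation (all inputs assumed).** Three progressive states (before first progression, second treatment, after last progression), toxicity not separated, every progressor crossing over, 100,000 patients per scenario. Monthly hazards: progression 0.06 in each step; death 0.008, 0.02 and 0.10. Utilities 0.80, 0.75 and 0.60. Two-year OS is about 58%. Zeros go only to states after the one in which the patient died or was lost. Patients alive and progression-free at 24 months receive none.

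| Loss over 2 years | Mean months in states 1 / 2 / 3 | q, state 2 | q, state 3 | Score with zeros | Score, reached only | True score |
|---|---|---|---|---|---|---|
| none | 11.82 / 5.80 / 2.06 | 0.118 | 0.377 | 14.07 | 15.05 | 15.05 |
| 5% | 11.82 / 5.84 / 2.05 | 0.144 | 0.415 | 13.92 | 15.06 | 15.06 |
| 15% | 11.85 / 5.78 / 2.05 | 0.198 | 0.494 | 13.58 | 15.04 | 15.04 |
| 25% | 11.83 / 5.81 / 2.03 | 0.251 | 0.557 | 13.27 | 15.04 | 15.05 |

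The 5% row by hand: 0.80 × 11.82 + 0.75 × 0.856 × 5.84 + 0.60 × 0.585 × 2.05 = 9.46 + 3.75 + 0.72, or about 13.92.

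**Effect on the arm difference.**

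- Identical disease, 5% against 15% loss: 13.92 − 13.58 = 0.34 months of false difference.
- Identical disease, 5% against 25% loss: 13.92 − 13.27 = 0.65 months.
- Equal 5% loss, with one better-surviving arm (progression hazards 0.035 and 0.045; death 0.006, 0.015 and 0.10; 2-year OS 72%): durations 15.28 / 4.72 / 1.16, zero shares 0.190 and 0.497, score 15.44 with zeros and 16.46 without. The difference from the 5% row is 15.44 − 13.92 = 1.52, against a true 16.46 − 15.06 = 1.40, so the shift is +0.12.

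In that last case the better-surviving arm has the larger zero shares, because fewer of its patients reach the later states, but it also spends less time there. The products nearly cancel: 0.190 × 0.75 × 4.72 + 0.497 × 0.60 × 1.16 = 1.02, against 0.144 × 0.75 × 5.84 + 0.415 × 0.60 × 2.05 = 1.14.

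**The case against.** The best defence is that no sentence says the zeros are averaged into the group weight. That follows from combining the special notes with the definition of the weight, and the missing-data paragraph can be read as keeping them out. On that reading there is no bias. This stands as far as it goes, but that paragraph is written for patients who reached a state without an EQ-5D; a patient who died earlier has an assigned value. The formula gives a utility no place to act except the group weight. Zeros would be harmless if utility and time were multiplied patient by patient, but the plan multiplies arm means. So either the rule acts and is wrong, or it is inert and contradicts the paragraph that governs.

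It is also fair to say that the effect may be small. Section 9.3 expects few patients to be censored before 2 years, and the larger figures above need 15–25% loss in one arm against 5% in the other. That expectation concerns survival status, however, and Section 9.8.2 itself allows that attrition may differ between arms.

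Three stronger inferences are tempting, and the documents do not support them:

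- **That the planned 70% against 50% 2-year OS implies a sizeable bias in a known direction.** The sign depends on the balance of q × u × T, as the last case shows. A separate five-state run, whose hazards are also assumed and not listed here, had 2-year OS of 69–73% against 52–54%; the shift ran from −0.05 to +0.13 months over six scenarios.
- **That everyone who dies without reaching the second treatment gets a zero for TOX2 and TWiST2.** A patient who progresses, never crosses over and dies is already in PROG, which runs from the last progression. No later state remains to score.
- **That loss is treated as death throughout.** It is censored in the durations; only the weight is affected.

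The last note probably lost the word "not". It is a wording error without a quantified effect.

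**Conclusion.** Wrong as written. If the zero rule is applied, it lowers each arm's score, by about 1.0 month with no loss (15.05 − 14.07) and 1.8 months with 25% loss (15.05 − 13.27) in the assumed scenarios. The A − B difference moves by about 0.1 months when loss is equal, and by 0.34 to 0.65 months with 5% against 15–25% loss, in favour of the arm with less loss. These compare with a clinically important difference of 2.4 months. Every size rests on assumed hazards, utilities and loss rates, since the documents do not give the share of patients who would receive zeros. The simulated arms had 2-year OS of 72% and 58%, not the planned 70% and 50%. The algebra does not depend on those assumptions.

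If the missing-data paragraph governs instead, the fault is a contradiction that leaves the primary PRO calculation undefined. The text needs correcting either way.

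**What to change.** Amend Section 9.8.2 before the Q-TWiST analysis is run:

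1. Delete both sentences that assign zero utility, for death and for withdrawal or loss.
2. State that each group utility uses only EQ-5D assessments made while the patient is alive and in that state within 24 months, in line with the missing-data paragraph.
3. State that death and censoring act only through the Kaplan-Meier durations.
4. Treat utilities unobserved because of withdrawal or loss as missing. Add a sensitivity analysis for informative loss, because the existing one covers reached states only.
5. Correct the last note so that utilities from states entered after 2 years are not used.

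The cost is a few sentences and slightly more analysis work, with no new data collection.

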10.1 Sample Collection and Submission Schedule

Samples are to be submitted as follows:

- Pretrial diagnostic pathology samples must be submitted within one (1) month of registration. See Section [10.2](#).
- Peripheral blood samples are to be submitted as outlined in Section [10.3](#) on the day of collection. Samples are to be collected at the following time points for each tube type:
 - Prior to start of treatment (yellow top at baseline only)
 - Every week for patients with grade 3 or 4 irAEs until the irAE resolves to grade 1 and then at the patients' regularly scheduled visits until they are tapered off
 - Every six (6) weeks (initial and crossover)
 - Time of Crossover
 - Time of Progression

10.2 Submissions to the ECOG-ACRIN Central Biorepository and Pathology Facility (CBPF)

Submitting pathologist and clinical research associate may refer to [Appendix I](#) which outlines the Pathology Submission Guidelines. Submission of pretrial diagnostic pathology samples from all patients is mandatory. Failure to submit the required materials may render the patient's data unevaluable.

The tissue samples are to be labeled with the Pathology ID as well as the information above.

10.2.1 Required Materials

Forms: Must be submitted with all tissue submissions.

- STS generated shipping manifest form
- ECOG-ACRIN Generic Specimen Submission Form (#2981) completed. Please identify the clinical status of the submitted material (i.e., pretreatment as opposed to remission and relapse).
- Copy of the pathology report

Pathological Material Submission:

- Representative diagnostic FFPE primary and metastatic tumor tissue blocks

NOTE: If a block is unavailable for submission, cores and slides are to be submitted. All cores and slides must be adequately labeled, with slides numbered sequentially in the order cut. Alternative submission per tissue availability:

- One (1) H&E slide from each source block, and
- Ten (10) - twenty (20) 5 µm unstained, uncharged, air-dried plus slides from the thickest part of the tumor, and
- One (1) or more core punches (minimum of 4mm diameter). If core punch tool is unavailable, request core punch kit from the ECOG-ACRIN CBPF [name]. Adequately label every slide and core submitted.

If these criteria cannot be met, please contact the ECOG-ACRIN Central Biorepository and Pathology Facility (CBPF) ([contact]) to obtain alternative submission requirements.

Rev. 6/16
Rev. Add10

10.2.2 Shipping Procedures

Pathology materials are to be shipped at ambient temperature within one (1) month following patient registration.

Ship using the CBPF's FedEx account using the FedEx on-line ship manager.

Ship to:

MD Anderson Cancer Center CBPF
[name]
[name]
[name]
[name]
Phone: Toll Free [name] [contact] Local or International Sites)
[contact]
Email: [contact]

Access to the FedEx shipping account for shipments to the ECOG-ACRIN CBPF at MD Anderson Cancer Center can only be obtained by logging onto fedex.com with an account issued by the ECOG-ACRIN CBPF. For security reasons, the account number will no longer be given out in protocols, over the phone, or via email. If your site needs to have an account created, please contact the ECOG-ACRIN CBPF by email at [contact]

Pretrial diagnostic pathology materials will be forwarded to [name] for central review.

10.3 Submissions to Immunologic Monitoring and Cellular Products Laboratory (IMCPL)

Blood samples should be shipped the day they are drawn. If you have any questions concerning sample collection and shipment, please contact the ECOG-ACRIN Study Coordinator at [contact] at the IMCPL.

NOTE: Blood should **NOT** be collected or shipped on Fridays.

Instructions to order kits are outlined in Section [10.3.1.1](#).

Submit from patients who answer “Yes” to “I agree to have my samples collected and I agree that my samples and related information may be used for the laboratory studies described above.”

Rev. 6/16

10.3.1 Sample Preparation Guidelines

Please completely fill all blood tubes as full as possible and collect the correct number and tube type as outlined below.

Each tube must be clearly labeled to include:

- ECOG-ACRIN protocol number EA6134
- ECOG-ACRIN five-digit patient sequence number
- Patient initials
- Originating institution/investigator name
- Date and time drawn
- Collection time point

At EACH time point please submit the following:

- TWO (2) FULL 10 cc RED top tubes (BD cat #367820 or SST 367988 gel separator/gold top/tiger tubes if the center can centrifuge them)
- Five (5) FULL 10 cc GREEN top heparin tubes (BD cat # 366480)

At Prior to Start of Treatment ONLY please submit the following:

- One (1) FULL 10 cc YELLOW top ACD tube (BD cat # 364606)

10.3.1.1 Shipping Kits

Shipping kits are available to order for the collection of the blood samples, and will contain the supplies and instructions for collecting, processing, and shipping the samples. To order kits please fax the request using the Shipping Kit Request Facsimile Form ([Appendix VII](#)) to [contact] or call the IMCPL at [contact]. Please allow ten (10) working days for shipment and provide the following information:

- Study Number
- Participating Site Number
- Contact Person and Telephone Number

The kits will be shipped via FedEx Express Saver. Please plan ahead, **priority overnight shipment is not possible.**

All blood samples should be shipped the day of collection using the shipping kit. Follow the shipping instructions provided in the kit carefully.

The shipping kit consists of the following:

- Insulated shipping container and packing material
- FedEx Priority Overnight return label
- Shipping instructions
- Shipping Kit Request Form

